## 7) Data Management

De-identified data will be analyzed using IBM SPSS and GraphPad Prism statistical analysis software. Data will be reported as the correlation between pain scores and physiological data recorded from the FitBit V3.

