## 2) Objectives

The primary objective of this study is to assess the feasibility of using virtual reality goggles to modulate pre-operative anxiety and intraoperative pain during vasectomy. Feasibility will be measured via the following parameters:

Pain will be quantified in the following manner:

- Pre-operative, intra-operative, and post-operative physiological parameters (heart rate, temperature, oxygen saturation) measured by FitBit Versa 3 device
- Numeric pain scale pre- and post-vasectomy

Anxiety will be measured in the following manner:

- Pre- and post-vasectomy State-Trait Anxiety Inventory (STAI) anxiety score

Feasibility will be further measured via subjective post-procedure satisfaction surveys. Further discussion of data analysis is detailed in the Research Procedures and Data and Specimen Banking sections of this protocol.

The secondary goal of this study will be to evaluate the effectiveness of interactive virtual reality versus static virtual reality in reducing pain during the procedure. Secondary objectives will be assessed using the same outcome measures as primary objectives. This study will attempt to expand the use of SmileyScope virtual reality goggles, which have already been proven to reduce procedural pain in the pediatric population.

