## 5) Procedures Involved

### Study Design

Patients will be randomized into one of three groups (interactive virtual reality, static virtual reality, and no virtual reality). Randomization sequence will be generated using a validated random number generator, and allocation concealment will be achieved via opaque envelope.

To ensure adequate power, the intended sample size has been calculated using the ANCOVA statistical test. Using G\*Power 3.1.9.4 software, a medium effect size 0.25, alpha 0.05, power 0.8, 3 groups and 1 covariate, the required sample size is 162 patients (54 patients per group, 1:1:1 ratio). No loss to follow up is anticipated.

All patients will be asked to wear the FitBit Versa 3 in the waiting room before the procedure. Patients randomized into one of the two virtual reality groups will be asked to wear the virtual reality goggles in the procedure room before the vasectomy. Before and after the procedure, a survey will be used to assess anxiety. Before the procedure, patients will also be asked to complete a pain scale survey to quantify baseline pain. After the procedure, patients will complete a pain scale survey to quantify their post-procedure pain. Physiologic data will be extracted from the FitBit device before, during, and after the vasectomy.

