### Research Procedures

All patients will be provided a FitBit Versa 3\* device which will be worn continuously during the pre-operative and intra-operative period. If randomized into one of two virtual reality groups, they will also be provided one pair of SmileyScope VR goggles\* to wear. Physiologic data associated with subjective pain and peri-operative anxiety is of interest to the study team (i.e., heart rate, skin

temperature, oxygen saturation). Physiologic data during the pre-operative period will be used as a baseline to measure changes in intra-operative pain. Pre-operative anxiety will be assessed via a modified six-item State-Trait Anxiety Inventory (STAI-6) anxiety questionnaire scored from 0-24. The STAI-6 has been previously validated in the assessment of anxiety in surgical patients. Physiologic data will be correlated with subjective measures of average or maximal intra-operative pain (numeric pain scale; 0-10) and anxiety (STAI-6; 0-24). Effectiveness of the VR goggles in managing intraoperative pain will also be assessed by post-operative satisfaction surveys.

\*Participants will not be held responsible for damaged or lost equipment provided by the study team. If any of the provided research hardware is damaged or deemed missing by the participant during the study period, replacements will be provided. Participants will be asked to return the FitBit Versa 3 and SmileyScope device after the procedure. The device will have a generic account associated with it, and data will be extracted from the device immediately after the procedure and deleted from the device.

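### The stated reporting rule is a pain–FitBit correlation with no arm term, and nowhere is the analysis comparing the three randomised arms specified, although the trial is sized on a 3-group ANCOVA

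*Combined protocol and SAP*

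**What the plan says.** All references are to the combined protocol and SAP.

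- **Section 7, Data Management**, after naming the software: "Data will be reported as the correlation between pain scores and physiological data recorded from the FitBit V3".
- **Section 5, Research Procedures**, gives three further uses of the data: "Physiologic data will be correlated with subjective measures of average or maximal intra-operative pain" (and with anxiety); "Physiologic data during the pre-operative period will be used as a baseline to measure changes in intra-operative pain"; and "Effectiveness of the VR goggles in managing intraoperative pain will also be assessed by post-operative satisfaction surveys". None is stated by arm.
- **Section 5, Study Design**, randomises 1:1:1 to interactive VR, static VR and no VR. It says "the intended sample size has been calculated using the ANCOVA statistical test", with "a medium effect size 0.25, alpha 0.05, power 0.8, 3 groups and 1 covariate", giving 162 patients, 54 per group. The outcome and the covariate are not named.
- **Section 2, Objectives**, sets the secondary goal: "evaluate the effectiveness of interactive virtual reality versus static virtual reality in reducing pain during the procedure". It adds: "Secondary objectives will be assessed using the same outcome measures as primary objectives". For the analysis it refers the reader to Research Procedures and to Data and Specimen Banking.
- **Section 6, Data and Specimen Banking**, lists data items, adverse effects and storage. It contains no test or model.

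**The concern.** A randomised trial earns its inference from comparing the arms as allocated. Here the only sentence on how results will be reported describes an association between two measurements, and the sections to which the Objectives send the reader do not supply the missing comparison.

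If reporting follows Section 7 as written, the interactive-versus-static goal goes unanswered and the test for which 162 patients were recruited is not reported. If the investigators instead run an ANCOVA, as the sizing suggests, they would have to choose its outcome, covariate and contrasts without a pre-stated rule, possibly with the data in view. A favourable result could not then be told apart from a favourable choice.

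**Working it through.** **1. Reproduce the sample size.** Inputs from Section 5, Study Design: f = 0.25, alpha 0.05, power 0.80, 3 groups, 1 covariate. Two things are assumed because the document is silent: f is on the residual SD scale of the ANCOVA, and the test is the overall one with 3 − 1 = 2 numerator degrees of freedom.

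- Noncentrality: lambda = N × f² = 162 × 0.0625 = 10.125.
- Denominator df = N − groups − covariates = 162 − 3 − 1 = 158.
- Power = P(noncentral F(2, 158, lambda) > the 5% critical value) = 0.813.
- Smallest N for 80%: 157 gives 0.799 and 158 gives 0.802, so 158, or 159 with equal arms.
- The stated 162 exceeds 158 by 4, and 4/158 = 2.5%, so the figure reproduces closely.
- With 1 numerator df the requirement would be 128 (129 with equal arms), which does not match.

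The stated N therefore fits an overall comparison of all three arms.

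**2. Look for that comparison among the stated analyses.**

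| Place | What is stated | Compares arms? |
|---|---|---|
| Section 7 | Correlation of pain with FitBit data | No |
| Section 5, Research Procedures | Correlation of FitBit data with pain and anxiety | No |
| Section 5, Research Procedures | Pre-operative physiology as baseline for change | No; a within-patient change |
| Section 5, Research Procedures | Satisfaction surveys as a measure of effectiveness | Not stated by arm |
| Section 5, Study Design | 3-group ANCOVA | Named for sizing only |
| Section 2 | Interactive versus static VR | An objective; no analysis attached |
| Section 6 | Data items, adverse effects, storage | No |

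**3. Can the correlation stand in for the comparison?** No. A pooled correlation is computed from pairs of pain score and FitBit value. Reassigning the arm labels among the 162 patients leaves every pair, and so the coefficient, unchanged. A statistic that is the same under every allocation cannot estimate an effect of allocation.

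**4. What is left open.** Section 6 collects two intra-operative pain items, maximum and average, and Research Procedures joins them with 'or'. Two natural covariates are collected before the procedure: baseline pain and the six-item anxiety score (STAI-6). That already gives 2 × 2 = 4 different ANCOVAs of pain that fit the sizing description, before any choice of contrasts or of an anxiety or FitBit outcome.

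**5. What the 80% refers to.** f = 0.25 fixes the overall spread of three means. It does not fix any single difference between arms, which depends on the pattern of means, and the document gives no pattern. The planned power therefore belongs to the overall test only.

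**6. Timing of the anxiety score.** Study Design has goggles put on in the procedure room before surgery and an anxiety survey before surgery, without ordering the two. Only the pre-procedure FitBit collection is placed in the waiting room. A pre-procedure STAI-6 taken with goggles on is affected by treatment and cannot serve as a baseline covariate.

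**The case against.** The strongest reply is that an arm comparison is plainly intended. The sizing names a 3-group ANCOVA, the Objectives name interactive versus static VR, and the sentence on satisfaction surveys says that effectiveness will 'also' be assessed that way, which implies other measures of effectiveness. Section 7 is a two-sentence data-management section and does not say that the correlation is the only result to be reported.

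Much of this stands, and it limits the point in two ways. A reader might infer that no arm comparison is mentioned anywhere; the Objectives contradict that, since interactive versus static VR is stated there as a goal. A reader might also infer that the arms will never be compared; the document does not say so, and the loss of the objective follows only if Section 7 is applied literally. What survives is that intention is not specification: no section turns the sizing test or the objective into an analysis.

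It may also be said that this is a feasibility study. But the Objectives measure feasibility through pain and anxiety and add an effectiveness goal, and Study Design sets 80% power for a group test.

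**Conclusion.** Wrong as written, and to be corrected before any data are seen. The only reporting rule contains no arm term, and the analysis comparing the randomised arms is not specified. This goes beyond missing detail, because following the stated rule would answer neither the overall test, which has 81% power at N = 162, nor the interactive-versus-static objective.

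The finding rests on the wording and on the fact that a correlation ignoring arm carries no treatment contrast. The power figure rests on the two assumptions in step 1 of the working.

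Two stronger conclusions might be drawn and are not supported. The sample size is not wrong: it reproduces for the overall test. Nor do the documents show that a particular contrast is underpowered by a particular amount, because any such figure needs an assumed pattern of arm means that they do not give. They support only the statement that the planned power does not carry over to each contrast.

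**What to change.** Replace the reporting sentence in Section 7 with text such as:

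> The main analysis is an ANCOVA of intra-operative pain (0–10; either the maximum or the average item, named before any data are seen) on randomised arm. Each patient is analysed in the allocated arm, with one pre-named covariate measured before goggles are worn. The overall 3-arm test at the 5% level is reported first. Adjusted differences with 95% confidence intervals follow for interactive versus static VR and for VR versus no VR (pooled or each VR arm, as pre-named by the sponsor). These contrasts are tested only if the overall test is significant, or under another pre-stated multiplicity rule. STAI-6 is compared by arm as a secondary outcome. The pre-procedure score is an outcome if taken with goggles on, and a baseline covariate only if taken before. The pain–FitBit correlation is exploratory.

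Add to Study Design that the 80% power applies to the overall 3-arm test and not to each contrast.

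The choice of pain item, covariate, form of the VR-versus-none contrast and multiplicity rule belongs to the sponsor, provided it is fixed in advance. Because the primary objective names pre-operative anxiety, the sponsor should state openly that STAI-6 is secondary and should fix when the pre-procedure score is taken relative to the goggles.

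Cost: more analysis wording and a written timing rule for STAI-6. No new data are needed, and N stays at 162 with pain as the single primary outcome.

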## 8) Risks to Subjects

### Adverse Events and Serious Adverse Events

An adverse event will be defined as any event that may harm the subject or require the subject to seek medical attention, and a serious adverse event will be defined as adverse events that require the subject to seek medical attention and may be life threatening.

Adverse events include dizziness, nausea, vomiting, or falls during or immediately after wearing the VR headset.

A serious fall during or immediately after wearing the VR headset constitutes a serious adverse event. Seizures constitute a serious adverse event. However, this is highly unlikely, as the VR scenarios developed do not present the flashing visual stimuli associated with seizures. In addition, patients with epilepsy and other seizure disorders will be excluded from the study.

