## 3) Background

Vasectomy is a safe and effective procedure for permanent sterilization in males. More than 500,000 vasectomies are performed annually in the United States, and that number is expected to grow rapidly in the coming years. The procedure is safe and can be quickly performed in an outpatient setting. Complications of vasectomy are rare, and can include hematoma and infection, spermatic granulomas, and post-vasectomy pain syndrome in rare cases. Like all outpatient surgical procedures where the patient is not under general anesthesia, vasectomies involve intraoperative and immediate post-operative pain. While use of the no-scalpel technique and local anesthetic reduces intraoperative pain, expected operative pain is still one of the main reasons patients cite for not undergoing the procedure.

In our current study, we aim to further modulate intraoperative pain using virtual reality goggles. In clinical trials, the SmileyScope device has been shown to reduce procedural pain in the pediatric population during venipuncture or intravenous cannulation. Results from those studies showed a statistically significant reduction in pain during intravenous procedures in the emergency department. This VR headset is undergoing study for approval by the U.S. Food and Drug Administration (FDA) to reduce pain and anxiety in patients aged 4 years and older undergoing needle blood draw or injection procedures. Currently, this device has been granted entrance to the FDA Safer Technologies Program. In this study, the SmileyScope virtual reality interface is

considered an investigational device because it is not yet approved for use in adult males undergoing vasectomy. We aim to use this same virtual reality modality to reduce pain during vasectomies.

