## Time Period of Data under Review

Data will be collected at enrollment, and during the procedure. Information will be kept for 3 years. De-identified data will be stored in a secure database for the duration of the study.

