## 6) Data and Specimen Banking

The following datapoints will be collected at initial clinic visit:

- Medical Record Number
- Age
- Date of Birth
- Sex
- Race/Ethnicity
- Marital Status
- Medical History
- Medications

The following data will be collected pre-procedure:

- Numerical anxiety scale survey (Modified 6-term STAI-S anxiety scale)
- Baseline pain measure
  - o “Please rate your current pain from 0 (no pain) to 10 (worst pain imaginable).”
- Physiologic data provided by FitBit Versa 3 – Data collected pre-procedure in waiting room. Data will be collected continuously during the time the patient is wearing the device. Data will be extracted from the FitBit after the procedure is finished and the patient has left.
  - o Heart Rate
  - o Oxygen saturation
  - o Skin temperature

The following data will be collected post-procedure:

- Length of procedure (start and end time)

- Numerical anxiety scale survey (Modified 6-term STAI-S anxiety scale)
- Numerical pain scale survey:
  - o Maximum pain felt during the procedure: "Please indicate the highest intensity of pain during the procedure on a scale of 0 (no pain) to 10 (worst pain imaginable)"
  - o Average pain felt during the procedure: "Please indicate the average intensity of pain during the procedure on a scale of 0 (no pain) to 10 (worst pain imaginable)"
- Post-procedure satisfaction:
  - o "How satisfied were you with today's procedure?"
  - o "If your urologist was using VR, would you be more or less likely to have the procedure?"
  - o "If your urologist was using VR, how likely would you be to recommend them to a friend undergoing the same procedure?"
  - o "How helpful was VR in managing your vasectomy today?"
  - o "Do you have any comments on today's procedure?"
    - Free text form for patient comments
  - o All questions will be answered via a 5-point Likert Scale as below:
    - 5 – Very Satisfied
    - 4 – Somewhat Satisfied
    - 3 – Neither Satisfied nor Dissatisfied
    - 2 – Somewhat Dissatisfied
    - 1 – Very Dissatisfied
    - 0 – Not applicable / Decline to Answer
- Physiologic data provided by FitBit Versa 3 - Data collected during the procedure and after the procedure in the waiting room
  - o Heart Rate
  - o Oxygen saturation
  - o Skin temperature

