- Adverse effects associated with goggles. Adverse effects are anticipated to be mild and not more than minimal risk. Patients can remove headsets at any time they wish, and adverse effects are anticipated to resolve with headset removal. Most common adverse effects include dizziness and nausea.

De-identified data will be stored in a secure database for 3 years.

- **Secure Storage:** Data will be housed in a HIPAA-compliant secure storage system, like REDCap or Box, within the University of Miami network with access restricted to approved members of the research team.
- **Limited Access:** Private identifiable information will be accessible only to IRB approved study team members with current IRB training.
- **Storage of Physical Records:** Physical records will be maintained for this study at a secure location where access is limited to approved personnel. The records will not be removed from University of Miami premises.
- **Storage of Specimens:** Specimens will be maintained for this study at a secure location where access is limited to approved personnel. The specimens will not be removed from University of Miami premises.

- **Retention/Destruction of Study Materials:** Study data/materials will be kept and/or destroyed according to applicable policy.

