## 13) Confidentiality

- **Secure Storage:** Data will be housed in a HIPAA-compliant secure storage system, like REDCap or Box, within the University of Miami network with access restricted to approved members of the research team.
- **Limited Access:** Private identifiable information will be accessible only to IRB approved study team members with current IRB training.
- **Unique ID Numbers and Coding:** Each patient will be assigned a unique ID number. The linking list will be kept secure. Direct identifiers listed in section 8 will be separated from the study materials (data and/or specimens) as soon as possible. During data abstraction, name and/or MRN are required for data verification purposes. After data abstraction is complete and data have been verified, the name will be removed (if collected). Only the MRN will be used to link the study ID/code to the individual after that point until the linking list is destroyed.
- **Destroying Identifiers:** The identifiers and the linking list will be destroyed as soon as scientifically possible and maintained only as long as necessary to abstract, analyze and verify data.
- **Storage of Physical Records:** Physical records will be maintained for this study at a secure location where access is limited to approved personnel. The records will not be removed from University of Miami premises.
- **Storage of Specimens:** Specimens will be maintained for this study at a secure location where access is limited to approved personnel. The specimens will not be removed from University of Miami premises.

- **Retention/Destruction of Study Materials:** Study data/materials will be kept and/or destroyed according to applicable policy.

The PHI to be accessed and reviewed is that which is minimally necessary to achieve the goals of this research. This includes:

- Medical Record Number
- Name
- Address (All geographic subdivisions smaller than a State, including street address, city, county, precinct, zip code)
- Telephone number
- Email address

Choose the statements below that are applicable to this research:

15(a).  Data will be collected from the EMR or subjects at UHealth.  
 Research Subjects will sign a HIPAA Authorization before the research will collect this data.  
(Complete Section 17 below)

15(b). Data collected:  
 Will include Protected Health information or Personally Identifiable Information

15(c). How will the research store the data?  

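### The adverse event definition is broader than the data the plan collects: no collection is described after the post-procedure waiting room, and the only safety item has no counterpart in the no-VR arm.

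*Combined protocol and SAP*

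**What the plan says.** **Definition.** Section 8, Adverse Events and Serious Adverse Events, opens with "An adverse event will be defined as any event that may harm the subject or require the subject to seek medical attention". The examples that follow are narrower: "Adverse events include dizziness, nausea, vomiting, or falls during or immediately after wearing the VR headset". A serious fall in that same window and a seizure count as serious; the seizure carries no stated window.

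**Collection period.** Section 5, Time Period of Data under Review, states: "Data will be collected at enrollment, and during the procedure". Section 6 goes slightly further, with FitBit data described as "Data collected during the procedure and after the procedure in the waiting room". No later call, visit or record check is described.

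**Safety data item.** The post-procedure list in Section 6 has one: "Adverse effects associated with goggles".

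**Known complications.** Section 3 says: "Complications of vasectomy are rare, and can include hematoma and infection, spermatic granulomas, and post-vasectomy pain syndrome in rare cases".

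**Reporting.** Section 14 sends any adverse events to the IRB under its reporting policy. It gives no end date and no method for finding events.

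**Records and link.** Section 13, item 15(a), provides for this source under a signed HIPAA authorization: "Data will be collected from the EMR or subjects at UHealth". On the link between code and person, Section 13 says "The identifiers and the linking list will be destroyed as soon as scientifically possible", but the same sentence keeps them for as long as abstraction, analysis and verification need them.

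**The concern.** A definition that includes any event leading a patient to seek care covers events after he has gone home. Nothing in the data plan looks for those. The mismatch is one of scope as well as time. A control patient who felt dizzy or nauseated on the day meets the Section 8 definition if the event may have harmed him, but no item in Section 6 would record it, because he wore no goggles.

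What is at stake is the meaning of the safety count. Section 3 calls the headset investigational for this use, and it is worn during a procedure done without general anesthesia. If the report lists few or no events, the reader cannot tell whether they did not occur or were not sought. For same-day symptoms, the control column would be empty by construction.

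**Working it through.** The documents state no safety figure to reproduce, so the main check sets the sections side by side. The arithmetic afterwards is illustrative.

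**1. Scope of definition against scope of collection**

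| Feature | Section 8 definition | Sections 5 and 6 collection |
|---|---|---|
| Time | No limit | Enrollment, procedure, waiting room afterwards |
| Relation to device | Not required | Goggle-associated only |
| Arms | All subjects | No evident counterpart for no VR |
| Method after discharge | None stated | None stated |

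That collection stops in the waiting room is an inference. The safety item itself carries no time stamp, but no section describes anything later. Section 14 governs what happens to an event once known and adds no way of learning of it.

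**2. Group sizes**

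Section 5, Study Design, gives 162 patients, 54 per group, from ANCOVA with f = 0.25, alpha 0.05, power 0.80, 3 groups and 1 covariate. With noncentrality f² × N, df1 = 2 and df2 = N − 4, the smallest N is 158 (power 0.802), or 159 with equal groups (power 0.805). The stated 162 gives power 0.813. The figure is close and not in dispute; it only supplies the denominators 54, 108 (both VR arms) and 162.

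**3. How many later events there might be**

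The documents say only that complications are rare, so the rate p is an assumption. Expected events are n × p; the chance of at least one in an arm is 1 − (1 − p)^54.

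| Assumed p | Expected per arm (n = 54) | Expected in all 162 | Chance of at least one in an arm |
|---|---|---|---|
| 1% | 0.5 | 1.6 | 42% |
| 2% | 1.1 | 3.2 | 66% |
| 5% | 2.7 | 8.1 | 94% |

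**4. What zero recorded events would mean**

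With complete ascertainment, zero events in n patients gives a one-sided 95% upper limit of 1 − 0.05^(1/n): 5.4% for 54 and 2.7% for 108.

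If only a share q of events comes to light, and independently of each other, zero recorded events bounds p × q instead of p. For one arm of 54, the limit on p is 5.4% / q: 10.8% at q = 0.5 and 21.6% at q = 0.25. Both q values are assumptions. The plan gives no basis for any value of q, nor for taking q as equal across arms, so no limit on p can be stated.

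**5. What a complete table could not do**

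A doubling from an assumed 2% to 4% is 54 × 0.02 = 1.1 against 54 × 0.04 = 2.2 events per arm. That is far too few for a comparison, so the table would be descriptive only.

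**The case against.** The strongest defence reads Section 8 as a whole. Its examples concern headset wear and the moments after it, and Section 6 expects adverse effects to resolve once the headset is removed. On that reading the trial targets acute headset effects, and same-day collection fits. The primary objective is feasibility, Section 2 states no safety objective, and a table of a few events would not show whether VR affects surgical outcome. Participants are also the investigator's own patients at one site (Sections 10 and 12), so some later events will come to notice.

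Much of this stands. It makes the narrow scope plausible and limits what any remedy can deliver. But the definition itself says something wider, and the narrow reading still leaves the no-VR arm without a comparable item. Either the definition or the collection has to move.

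Three stronger readings are tempting but unsupported:

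- **A reader might infer that the link is destroyed after the procedure, so late events could not be assigned to an arm.** Section 13 keeps the list while abstraction, analysis and verification need it, with the medical record number as the link until then. Section 15 asks for early destruction of PHI but sets no date. While the list exists, a late event that is reported or found can be traced to its arm.
- **A reader might infer that nearly all later events would go unrecorded.** Capture would be passive and unsystematic, but the documents do not allow the missed share to be estimated.
- **A reader might infer that the headset causes movement and so surgical complications.** No section says or suggests this, and the point does not need it.

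**Conclusion.** The point holds as a mismatch between definition and collection. Followed as written, the plan cannot deliver the events that Section 8 defines, least of all in the no-VR arm. Later events would depend on spontaneous reports, so counts by arm would be incomplete and an absence of late events would carry no information.

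The number of events affected cannot be taken from the documents; 1.6 to 8.1 among 162 patients follows only from assumed rates of 1% to 5%. The conclusion does not depend on that range. It rests on the inference that no collection follows the waiting room, which no section contradicts. The efficacy analyses and the sample size are unaffected. It should be corrected in the protocol, but it does not threaten the trial's main objectives.

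**What to change.** Choose one of two routes and make Sections 5, 6 and 8 agree.

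- **If the wide definition is meant:** in Section 6, replace the goggles-only item with adverse events under the Section 8 definition, asked in the same way in all three arms, with goggle relation as a separate field. In Sections 5 and 6, add one EMR review per participant at a fixed interval after the procedure, for example 30 days. Cover the complications named in Section 3, falls, and unscheduled calls or visits. Tabulate by arm, descriptively, with no between-arm test.
- **If only acute headset effects are meant:** narrow the Section 8 definition to that window and state that the trial draws no conclusion on later complications. Same-day symptoms should still be asked of the no-VR arm if they are to be compared.

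Section 13 needs at most a note that abstraction includes the chart review, since it already keeps the linking list while abstraction continues.

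The first route costs protocol wording, one data form, a few minutes of chart review per patient, and somewhat longer retention of the link. It uses the EMR access already provided for in Section 13. Care received outside UHealth may be missed, and the report should say so. The second route costs only wording.
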